EMA is a survey approach which uses repeated sampling of participants to capture behaviors and experiences in a real time context. This methodological approach maintains the ecological validity of reported behaviors and decreases the impact of recall bias as surveys are sent periodically to participants through electronic devices.⁶¹ EMA is particularly useful when trying to understand the context around symptoms or behaviors. Available literature that combines the EMA methodology with asthma research focuses primarily on asthma-related outcomes such as symptoms, control, quality of life, history, and medication adherence and their relationship with stress (perceived stress, mood, hassles, social support).⁶²⁻⁶⁴ None of the published literature to date pairs EMA with indoor air quality and asthma symptoms. The ability to timestamp behaviors, events, experiences, whether they present a positive or negative health impact, is valuable when seeking to understand the complexity of multiple risk factors and multiple environmental and behavioral interactions.

Exposure	Sensor	Range/ Accuracy	Optimal range
VOCs	Multi-pixel metal oxide semiconductor gas sensor	0-60,000 ppb/ $\pm 10\%$	<333ppb
PM _{2.5}	Laser-based light scattering particle sensor	0-1,000 $\mu\text{g}/\text{m}^3$ / $\pm 15\mu\text{g}/\text{m}^3$ or 15%	<15 $\mu\text{g}/\text{m}^3$

Awair Omni Indoor Air Quality Monitor® continuously monitors about 1,000 square feet of indoor air for 7 air quality factors: total VOC, PM_{2.5}, temperature, humidity, CO₂, ambient light, and ambient noise. This feasibility study will only focus on VOCs and PM_{2.5} levels (Table 1). The Awair Omni measures about 4"X4"X1.3", is wi-fi and Bluetooth enabled, plugs into a standard AC outlet, and includes an 8-hour battery back-up. An air quality reading is taken every 10 seconds and real-time data are uploaded to a dashboard accessed only by research personnel. The display on the Awair Omni will be limited to VOCs and PM_{2.5} data. Our preliminary work with Awair indoor air quality monitors indicates that increased VOC levels are detected when disinfectants are used and increased PM_{2.5} levels are detected when vacuuming without a

[figure not shown]
[figure not shown]
vacuum cleaner.

HEPA filter. The Awair proprietary dashboard provides secure communication between the Awair Omni and its dashboard. Data will be exported from the dashboard to a .CSV file.⁶⁵⁻⁷¹

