4. During the 14-day data collection period, data from the EMA will be collected using EMA software platform on a personal smartphone (iOS or Android) and EMA software platform.⁷³ Each morning, participants will receive an EMA survey concerning asthma symptoms and a reminder to use their spirometer. Additionally, EMA surveys addressing disinfectant use, asthma symptoms, and spirometry will occur randomly twice/day (6am – 10pm) or tailored for those working off hours (Appendix).
5. A custom interface between the EMA platform and the Awair indoor air quality monitor will alert participants when levels of indoor VOCs or particulates are detected outside the optimal range (Table 1). The air quality monitor will communicate with the EMA platform using publicly available application programming interface (api). Upon notification from the Awair, the EMA will signal the participant to complete a brief survey on disinfectant use/air particulate exposure (depending on the alert), current asthma symptoms, and proximity to the Awair (Appendix). The EMA will then direct participants to use the spirometer. Participants experiencing symptoms will be guided to follow their asthma action plan/provider instructions.
6. Thirty minutes after VOC/PM_{2.5} notification, a second EMA notification will be sent for participants to complete a survey on mitigation strategies, respiratory outcomes, and spirometry use if not already completed (Figure 4).
7. Research personnel will monitor use of these devices/apps and contact participants if a 24-hour gap in data is noted to address concerns and determine acceptability. Research team members will check-in with each participant at about the 7-day mark to address technical concerns and ease of use.

8. At the end of the 14 days, participants will complete a short acceptability, appropriateness, and feasibility REDCap survey. A random sample of 20 participants will be interviewed to provide further insights.
9. Participants will be asked to return the Awair in the provided mailer. The Awair will be fully disinfected per manufacturer's directions. Participants will keep the Zephyr_x spirometer as an incentive.

Baseline Measures

The following measures will be administered at baseline via REDCap:

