- *EMA survey triggered by VOCs/PM_{2.5} greater than optimal range as detected by the Awair* will query asthma symptoms, lists of probable sources of elevated VOCs or PM_{2.5}.
- *EMA survey 30-minutes after Awair air quality notification* queries mitigation strategies used (from lists) and asthma symptoms.
- *Home spirometer use* (Yes:No) queried in each EMA survey

Home spirometer. FEV₁% predicted– a standard metric of lung function for those with asthma.

Seven-Day check-in. Open-ended questions to identify any trouble-shooting areas, determine if adjustments need to be made, and assess ease of use of the app/devices. Interactions will be recorded and reviewed by the research team for patterns and to identify any adjustments that are needed.

Participant feasibility assessment. At the end of the 14-day data collection period, participants will be asked to respond to a short REDCap survey assessing acceptability, appropriateness, and feasibility of the indoor air quality monitor, EMA notifications, and the home spirometer with response ranging from 1=completely disagree to 5=completely agree. A random sample of 20 participants will be interviewed to further explore these factors using open-ended questions such as "Tell us what you liked/didn't like about the indoor air quality monitor", "Describe the strengths/concerns about the survey you received about your home indoor air quality".

Data Analysis

Each day of observation will be divided into four 4-hour periods between 6 a.m. and 10 p.m. Data from a given period will be considered as follows:

1. Period specific data from all event-contingent EMA prompts [prompts triggered by high indoor air VOC/PM_{2.5} readings] will be analyzed. If multiple event-contingent prompts were answered, data will be averaged across all event-contingent prompts during that period.
2. Data from all answered baseline and random [signal-contingent] EMA prompts will be considered.

Aim 1. For this aim, we will assess:

1. Compliance with the EMA prompts as indicated by the frequency of responses to prompts, specifically:
 - a. # of responses (complete:incomplete)/number of prompts
 - b. # times spirometer used/number of prompts
 - c. # times environment modified/number of event-contingent prompts
2. Compliance as described in 1a-1c by 4-hr each period.

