We will also assess the duration the indoor air quality monitor is used by each participant. The quantitative participant feasibility assessment of acceptability, appropriateness, and feasibility will be analyzed descriptively. In addition, we will examine differences in use/acceptance by participant characteristics (e.g., age, asthma symptoms, overall health, education, etc). Qualitative interview data will be transcribed, uploaded into Dedoose qualitative analysis software for content analysis.

Aim 2a: We will collect baseline data on the current frequency and degree of disinfectants/cleaners and exposure to environmental triggers (e.g., secondhand smoke). We will capture real-time self-reported data on disinfectant use throughout the study period. We will determine the prevalence of disinfectant/cleaner use and frequency (% EMA prompts at which disinfectant/cleaner use is reported). We will obtain data from the Awair dashboard to determine the number of times VOCs and PM_{2.5} levels exceed optimal levels, average daily levels, average levels per time period, and fluctuations in VOC and PM_{2.5}. We will identify possible environmental triggers that contribute to high levels of VOCs and PM_{2.5} leading to event-contingent prompts.

[figure not shown]
Aim 2b: We will determine baseline level of asthma control as measured by the ACT. We will use EMA to determine the level of asthma control over the study period as indicated by (a) asthma symptoms reported at each prompt and over the 14 days; (b) number of time-periods during which an EMA prompt is sent and participants report asthma symptoms; and (c) lung function as measured by FEV₁% predicted at each prompt. Asthma control will also be evaluated using EMA by exploring differences in variability in lung function.

Aim 3: Data collected using the EMA approach are multilevel with time windows (level 1) nested with individuals (level 2). The exposure variables will include: (1) Baseline self-reported use and frequency of disinfectant/cleaner use and PM_{2.5} exposures; (2) Number of times VOC and PM_{2.5} levels exceed the threshold for the optimal readings per week; and (3) Average scores of VOC and PM_{2.5} levels in the time windows considered in the analysis. The outcome variables we will consider include occurrence of any asthma symptoms, inhaler use, and FEV₁% predicted (within 30 minutes of each EMA prompt).

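### The weekly exceedance count in Aim 3 is not adjusted for monitored time, and its week is not placed relative to the prompt-level outcome

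*Combined protocol and SAP*

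**What the plan says.** All references are to the combined protocol and SAP.

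- **Exposure.** Data Analysis, Aim 3, names three exposure variables. The second is the "Number of times VOC and PM_{2.5} levels exceed the threshold for the optimal readings per week". The third is the "Average scores of VOC and PM_{2.5} levels in the time windows considered in the analysis".
- **Outcomes.** These are momentary: "The outcome variables we will consider include occurrence of any asthma symptoms, inhaler use, and FEV₁% predicted (within 30 minutes of each EMA prompt". Time windows are level 1 and persons level 2, and Data Analysis opens with: "Each day of observation will be divided into four 4-hour periods between 6 a.m. and 10 p.m".
- **Covariates.** The Aim 3 models adjust for time of day, day of week, baseline symptoms, and demographic and psychosocial characteristics. Monitored hours are not listed.
- **Monitored time.** Under Aim 1: "We will also assess the duration the indoor air quality monitor is used by each participant". The same paragraph plans to compare use and acceptance across participant characteristics, and asthma symptoms are one of its examples. Nothing links this to Aim 3.
- **Gaps.** Procedures, step 7, has staff "contact participants if a 24-hour gap in data is noted". No analytic rule for gaps is given.
- **Sampling.** Data collection methods, Awair Omni: "An air quality reading is taken every 10 seconds". Table 1 gives the limits. Neither Aim 2a nor Aim 3 says what counts as one exceedance.

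**The concern.** A count per week is scaled to calendar time, not to time observed. An hour without readings can add no exceedances, so a home with patchy monitoring looks cleaner than an identical home with full monitoring. If uptime is unrelated to symptoms, this is measurement noise that tends to weaken an association. If uptime is related to symptoms, which the plan itself intends to look into, the count can show an association that has nothing to do with air quality.

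There are two further gaps. A weekly value is to be related to outcomes within 30 minutes of a prompt, but the plan does not say whether the week ends at the prompt, contains it, or is averaged over the study. Also, with readings every 10 seconds, the number of times above a limit could mean readings or episodes, so two analysts could derive very different variables. Aim 3 is exploratory, but its results are meant as preliminary data for a powered study, so the exposure should be one that a later team can reproduce.

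**Working it through.** The plan gives no numerical figure for this exposure, so there is nothing to reproduce. Steps 1 to 3 are arithmetic from the documents, with assumptions stated where used. Steps 4 and 5 are illustrations with assumed inputs.

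**1. Uptime.** Expected count = true rate × monitored hours, so the share of a week's count retained after a gap of g hours is 1 − g/168.
- g = 8: 1 − 8/168 = 95.2%
- g = 24: 1 − 24/168 = 85.7%, a loss of 14.3%
- g = 48: 71.4%
- g = 72: 57.1%

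At equal true rates, the ratio of counts equals the ratio of uptimes: 100% against 75% gives 1/0.75 = 1.33, and 100% against 50% gives 1/0.50 = 2.0.

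**2. Timing.** Suppose the week is a fixed study week and the exceedance rate is constant. For an outcome t days into the week, the share of the count falling after it is (7 − t)/7.
- Middle of day 1 (t = 0.5): 6.5/7 = 93%
- Mid-week (t = 3.5): 3.5/7 = 50%
- Middle of day 7 (t = 6.5): 0.5/7 = 7%
- Average over the seven days: 50%

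The alternative is a week ending at the prompt. With r usable run-in days, a full 7-day look-back exists on 14 − (7 − r) of the 14 days. That is 7 days with no run-in data and 10 with all three run-in days. For VOCs it is 8 to 9, since calibration takes 24 to 48 hours of the run-in.

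**3. Unit.** One hour above a limit is 3,600/10 = 360 readings, or one episode.

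**4. How much information is lost (assumed inputs).** True weekly episode rates are log-normal around 20 with log-SD 0.6, counts are Poisson, and uptime is uniform and unrelated to the rate. The table shows R² with the true log rate.

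| Uptime | Log count | Log count per monitored hour |
|---|---|---|
| 80–100% | 0.83 | 0.84 |
| 50–100% | 0.74 | 0.80 |
| 25–100% | 0.58 | 0.75 |

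A single 24-hour gap leaves 85.7% uptime, which lies in the first row, where almost nothing is lost.

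**5. What happens if uptime or later exposure is related to symptoms (assumed inputs).** Both simulations use 50 persons, 1,000 repeats, no true exposure effect, person-level linear regression and a nominal 5% test.
- *Uptime.* About 10 episodes per person and median uptime about 80%. With a correlation of 0, 0.3, 0.5 or 0.8 between the symptom trait and uptime (on the logit scale), the raw count is falsely significant in about 5%, 7%, 10% and 20% of runs. The count divided by uptime gives about 6%, 4%, 5% and 6%.
- *Timing.* Five episodes expected before and five after the outcome. If symptoms reduce later exceedances by 0, 20, 40 or 60%, a count spanning both sides is falsely significant in about 4%, 9%, 19% and 41% of runs. A count of prior exceedances only stays at about 3 to 5%.

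The documents give no value for either link. These runs show direction and mechanism, not the expected size in this study.

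**The case against.** The strongest reply is that this is one of three exposures in an exploratory aim of a feasibility study. The window average sits in the outcome's own window and is much less sensitive to uptime, and a time-stamped lag analysis is planned as well. Uptime may also be high: the monitor runs on mains power with an 8-hour battery, there is a 3-day run-in, staff act on 24-hour gaps, and there is a check-in at about day 7. At 80–100% uptime the correction gains almost nothing (0.83 against 0.84). All of this stands, and it limits the importance of the point.

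Three stronger readings are tempting and are not supported:

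- **That the plan uses exceedances occurring after the outcome.** A reader might infer this from a weekly count set against prompt-level outcomes. It follows for a fixed study week or a 14-day average, which are the plain readings, but the plan never defines the week, and a week ending at the prompt would avoid it. The defect is that timing is unspecified.
- **That missing readings are scored as clean air.** No such rule is written. The effect arises only because a count gains nothing from hours without readings and no adjustment is stated.
- **That uptime is known to differ by symptoms.** The plan intends to examine this and reports no result.

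It is also fair to say that a weekly count may be meant as a measure of overall burden between persons. That use is legitimate, but a person-level rate over the study also includes time after most outcomes. It should not be read as prior exposure.

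**Conclusion.** The point holds in limited form. As written, the second Aim 3 exposure falls when monitor time is lost, and the plan does not use the duration data it already collects to correct for this. The size depends on uptime: about 14% of a week for one 24-hour gap, two-fold between 100% and 50% uptime at equal true rates, and little effect above about 80%. The documents give no uptime figures, so anything larger rests on assumption. The average of one half of the count falling after the outcome rests on a fixed study week and a constant rate, neither of which the plan states. Whether bias, rather than noise, results depends on a link between symptoms and uptime or later exposure. The design makes such a link plausible, since alerts lead to questions about mitigation, but the documents do not quantify it. This is a free improvement to one exploratory exposure, and no confirmatory conclusion is at risk.

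**What to change.** In Data Analysis, Aim 3, restate the second exposure as follows.

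1. **Denominator.** Use exceedances per monitored hour, or keep the count and adjust for log monitored hours. Set periods with too little monitored time to missing, and state the minimum.
2. **Timing.** For within-person associations, count only exceedances before each prompt, over a stated look-back, and say how early study days and run-in data are handled.
3. **Between-person term.** Keep the person-level rate as a separate level 2 term, described as overall burden and not as prior exposure.
4. **Unit.** State whether an exceedance is a 10-second reading or an episode. If it is an episode, define its start and end. Use the same definition in Aim 2a.

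The look-back length, minimum coverage and episode cut-offs are for the sponsor to choose; the documents do not point to particular values. Reporting the distribution of uptime would show readers whether the correction mattered.

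The cost is a few sentences in the plan and a short derivation from the time-stamped CSV export already foreseen. No new data are needed.

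### Aim 3 does not say how the VOC/PM2.5 mean is timed against the outcome, and names no momentary self-reported exposure

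*Combined protocol and SAP*

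**What the plan says.** Data Analysis, Aim 3, treats time windows as level 1 and individuals as level 2, and names three exposures:

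1. Baseline self-reported disinfectant/cleaner use and PM2.5 exposures.
2. The number of times per week that VOC and PM2.5 exceed the optimal threshold.
3. "Average scores of VOC and PM_{2.5} levels in the time windows considered in the analysis".

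The list is worded as open. The outcomes are any asthma symptoms, inhaler use and FEV1% predicted, the last taken "within 30 minutes of each EMA prompt".

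Aim 3 does not define its windows. The opening of Data Analysis says: "Each day of observation will be divided into four 4-hour periods between 6 a.m. and 10 p.m". Aim 2a summarises monitor data as "average levels per time period", among other measures.

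For prompts triggered by high readings, Procedures step 5 says the interface "will alert participants when levels of indoor VOCs or particulates are detected outside the optimal range". Step 6 adds: "Thirty minutes after VOC/PM_{2.5} notification, a second EMA notification will be sent". If several such prompts are answered in one period, "data will be averaged across all event-contingent prompts during that period".

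Under EMA survey items, the random surveys ask about disinfectant/cleaner use in the last 2 hours. The analysis section names that item only under Aim 2a, as a prevalence and frequency. Specific Aims (Aim 3) and Innovation both intend self-reported exposure to be related to asthma control, and Innovation refers to real-time data.

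**The concern.** Baseline use is fixed within a person, and exceedances are counted by week. The window mean is the only named exposure that changes from moment to moment, so any within-person, short-term association rests on it. The 30-minute rule ties FEV1 to the prompt. It does not tie the air measurement to either.

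If the window extends past the prompt, the exposure contains air measured after the outcome. Time order is then unclear, and an association with the preceding air can be diluted. For alert-triggered prompts, one mean can mix air from before the alert, from the episode, and from after any mitigation.

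The lag-time analysis at the end of Aim 3 does not settle this. It covers only event-contingent prompts and symptoms, and it does not time the exposure in the regressions.

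The self-report side has a related gap. A baseline measure cannot inform a within-person association, and the EMA item that could is not named in the Aim 3 list. The results are meant as preliminary data for a powered study, so the definition of exposure may be carried forward.

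**Working it through.** The plan states no figure on this point, so there is none to reproduce. The calculation below is conditional on the windows being the 4-hour periods.

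**Inputs from the documents:** 240-minute periods; two random prompts a day between 6 am and 10 pm; FEV1 within 30 minutes of the prompt; a second survey 30 minutes after an alert; a reading every 10 seconds. **Assumption:** the prompt time *t* is uniform within its period.

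**Random prompts**

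- Share of the mean that follows the prompt: E[(240 − t)/240] = 0.50. The share varies widely: the 10th to 90th percentiles are 10% to 90%.
- Share that follows an FEV1 taken *d* minutes later: (240 − d)²/(2 × 240²). With *d* uniform on 0 to 30, this averages (240³ − 210³)/(3 × 30 × 2 × 240²) = 4,563,000/10,368,000 = 0.44. At *d* = 30 it is 44,100/115,200 = 0.38. If FEV1 may fall within 30 minutes on either side of the prompt, it is 0.50.
- If prompts are not uniform: 75% if all fall in the first half of a period, 25% if all fall in the second half.
- Share of a look-back of *L* minutes that lies before the period starts: L/480, so 12.5% for 1 hour and 25% for 2 hours.

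**Morning survey.** Its clock time is not given. The share that follows it would be 100%, 75%, 50% or 25% at 6, 7, 8 or 9 am.

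**Alerts, also assumed uniform within the period**

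- Before the alert: 0.50.
- Alert to the 30-minute survey: (30 × 210 + 450)/57,600 = 0.117.
- After that survey: 210²/(2 × 240²) = 0.383.
- The survey falls outside the alert's own period in 30/240 = 12.5% of cases.

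**Illustration of whether a look-back would measure better.** The documents give neither how long indoor levels persist nor which interval matters, so both are assumed. Levels follow a first-order autoregressive series on the log scale, with time constants of 30, 120 and 480 minutes. Entries are correlations with the air assumed to matter.

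| Air assumed to matter | Fixed 4-hour period | 2-hour look-back |
|---|---|---|
| Last 15 min | 0.49 / 0.76 / 0.92 | 0.52 / 0.79 / 0.94 |
| Last 2 hours | 0.63 / 0.80 / 0.93 | 1 by construction |
| Last 4 hours | 0.56 / 0.72 / 0.89 | 0.76 / 0.88 / 0.96 |

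The middle row favours the 2-hour look-back by definition and should carry no weight. In the first row the two are nearly tied, while a 1-hour look-back gives 0.74 / 0.91 / 0.98 and a 4-hour look-back only 0.34 / 0.61 / 0.87. Ending the window at the prompt helps, but its length matters as well.

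**The case against.** The strongest reply is that Aim 3 never adopts the 4-hour periods. The plan elsewhere writes of periods, and only Aim 3 writes of time windows considered in the analysis. A reader might infer that the plan commits to averaging air after the outcome. It does not: the window is undefined. This stands, and the 50% and 44% are therefore conditional. It does not remove the gap, because no other averaging window is given.

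Second, a same-window mean may be coherent for symptoms. Aim 2b counts symptoms by time period, and the symptom recall wording for random and morning surveys sits in an Appendix that is not in the text available here. As contemporaneous description the mean is usable. The timing gap is clearest for FEV1.

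Third, a reader might infer reverse causation, with symptomatic participants changing their air, or a definite loss of power. The documents count environmental modification only against event-contingent prompts and do not say that symptoms drive it. They give no effect size, persistence or relevant interval. Neither inference is supported beyond being possible.

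Fourth, a reader might infer that EMA-reported use is excluded from Aim 3. The list is open, and Specific Aims and Innovation point the other way. It is simply not named, so this half of the point is a clarification.

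Finally, no document shows that 2 hours is the right interval, and a badly chosen look-back can do worse than the period mean, as the 4-hour case shows. That argues for fixing the length in advance with a sensitivity analysis. It does not argue for leaving the window open.

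**Conclusion.** The point holds as a gap in specification. Nothing in the plan orders the VOC/PM2.5 mean relative to the outcome, and several different analyses would fit the text. On the only windows defined, and with uniformly timed random prompts, an average of 50% of the averaged air follows the prompt and about 44% follows an FEV1 taken 0 to 30 minutes later. The direction of concern is blurred time order and possible dilution; no size of bias or power loss is claimed.

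The self-report half holds as an omission: the named exposure cannot vary within a person, while a suitable item is collected and the aims intend its use.

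Importance is low to moderate. Aim 3 is exploratory, this is a feasibility study, and exported readings with time stamps allow any window to be computed later. It is a cheap improvement.

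**What to change.** State the following under Data Analysis, Aim 3:

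- **(a) Random and morning prompts.** Make the answered prompt, nested in person, the level-1 record. Use mean VOC and mean PM2.5 over a prespecified look-back ending at the prompt time stamp or, for FEV1, at the spirometry time stamp. An example is 2 hours, to match the EMA recall item, with 1 hour as sensitivity analysis. Let the look-back cross period boundaries.
- **(b) Event-contingent prompts.** Analyse them separately or with a prompt-type term, with one record per alert. Use the level at the alert and, for the 30-minute survey, the mean since the alert. A mean since the alert would cover almost no time for a promptly answered first survey.
- **(c) Self-report.** Add EMA-reported disinfectant/cleaner use in the last 2 hours as a level-1 exposure for random prompts. Keep baseline use at level 2.
- **(d) Same-window mean.** Keep it as a descriptive or secondary analysis, and define its window.

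**Cost:** plan wording and a little more data-management code. The 10-second readings, the time stamps and the 2-hour item are already collected. The look-back length is a choice that no document justifies biologically, so it must be fixed before the associations are examined. One record per alert also leaves records clustered within person and day, which the model must allow for.

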1. *Adult Asthma History* includes 5 items adapted from the Behavioral Risk Factor Surveillance System Survey.⁷⁴ Four items address participants' recent contact with healthcare professionals for asthma since COVID-19. The final item addresses changes in routine work/activities due to asthma since COVID-19.
2. *Asthma Control Test (ACT)*. The ACT includes 5 items addressing: asthma symptoms, use of rescue medications, and effect of asthma on daily functioning. Responses are summed for total ACT score.^{75,76}
3. *Airborne Exposures*. The 7 items from the PROMISSM Pool V1.0 Dyspnea Airborne Exposure address airborne allergens, pollutants, smoke, pets, and use of pesticides using Yes:No response options.⁷⁷
4. *Adult Asthma Adherence Questionnaire*,TM includes 5 items on following their prescribed asthma medication plan and barriers to following that plan.⁷⁸
5. *Health and Demographics* includes items such as self-rated physical health, comorbidities, height/weight, age, education, ZIP code, smoking status, and COVID-19 prevention practices, and COVID-19 exposure/infection status.
6. *Home Environmental Exposure* data will be gathered including home type, # of occupants, vacuum with HEPA filter, cleaning practices, cleaning products, air filter, heating, ventilation, smoke exposures, hand washing practices, pests, hobbies, odors, indoor plants, printers, flooring, and stove type.^{79,80}

We will also measure the following psychometrically valid measures as potential confounders:

7. *Emotional Distress-Anxiety and Depression PROMIS Short Forms 4a* assess anxiety and depression levels within the last 7 days (4 items). Higher scores indicate higher severity of anxiety or depression.^{81,82}
8. *Emotional Support*, PROMIS_SF_V2 Short Form 4A measures perceived feelings of support, being cared for and valued (4 items).⁸³ Higher score indicating a higher perceived emotional support.
9. *Perceived stress scale* includes 4 items measuring the degree to which situations in one's life are appraised as stressful.⁸⁴⁻⁸⁶ Higher scores indicate an increased level of perceived stress.

EMA survey items (See Appendix).

- *Asthma symptoms* (trouble breathing, wheezing, coughing, other symptoms [Yes:No]) assessed each time participants are asked to complete an EMA survey.
- *Random EMA surveys (twice/day)* assess use of disinfectants/cleaners in last 2 hours (Yes:No) if Yes, the type, brand, and asthma symptoms are queried.

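### Aim 3 symptom model: alerts add symptom questions to high-exposure windows, so an any-yes outcome per window can be associated with exposure when exposure has no effect

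*Combined protocol and SAP*

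**What the plan says.** **Unit, outcome and exposure.** Data Analysis, Aim 3, describes the data as "multilevel with time windows (level 1) nested with individuals (level 2"). The outcomes listed begin with "occurrence of any asthma symptoms", go on to inhaler use, and end with FEV1% predicted, followed by a parenthesis setting a half-hour limit around each EMA prompt. One of the three exposures is the average VOC and PM2.5 level "in the time windows considered in the analysis". The opening of Data Analysis defines the periods: "Each day of observation will be divided into four 4-hour periods between 6 a.m. and 10 p.m". Binary outcomes go into a multilevel logistic regression whose level 1 covariates are time of day and day of week.

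**When symptoms are asked.** Procedures, step 4, schedules one morning survey and two random surveys a day. Step 5 adds a survey that includes current symptoms when VOC or PM2.5 leaves the optimal range. Step 6 adds another half an hour later: "a second EMA notification will be sent for participants to complete a survey on mitigation strategies" and respiratory outcomes. EMA survey items says that symptoms are "assessed each time participants are asked to complete an EMA survey".

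**How answers are combined.** The opening of Data Analysis averages answers across the alert-triggered prompts answered in a period. Answers to baseline and random prompts are to be considered as well. Nothing says how the two sets are merged, how an average of yes/no answers becomes binary, or what happens to a window with no prompt.

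**The concern.** The exposure determines how often the outcome is looked for. A window with high VOC or PM2.5 triggers alerts, each alert brings further symptom questions, and each question is another chance of a yes. If the window outcome is yes whenever any answer is yes, the probability of a positive window rises with exposure even if symptoms have nothing to do with it. This would hold even if participants did not know that an alert had fired, so it is separate from any effect of the alert on reporting.

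Specific Aims presents the findings as preliminary data for a powered study, and the Summary says that they may affect recommendations on disinfectant use. A spurious positive association could mislead both.

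**Working it through.** The documents state no figure to reproduce: there is no symptom rate, alert rate, response rate, effect size or alpha for Aim 3. The mechanism follows from the text; its size rests on assumptions.

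**1. Counts from the plan.** 14 days × 4 windows = 56 windows per person. 14 days × 3 scheduled prompts = 42 scheduled prompts. At least 56 − 42 = 14 windows per person therefore have no scheduled prompt and yield a symptom answer only if an alert survey falls in them. One alert adds up to 2 symptom questions, so a window with one scheduled prompt goes from 1 question to 3.

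**2. Mechanism, with no exposure effect.** With k independent questions, each yes with probability p, P(any yes) = 1 − (1 − p)^k. At an assumed p = 0.2:

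- k = 1: 0.200
- k = 3: 1 − 0.8³ = 0.488
- odds ratio, 3 questions against 1: (0.488/0.512)/(0.2/0.8) = 3.81 (3.35 at p = 0.1, 4.47 at p = 0.3)

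With a beta-binomial within-window correlation of 0.5, P(any yes) at k = 3 is 0.328, and the odds ratio is (0.328/0.672)/0.25 = 1.95. At correlation 0.8 it is (0.249/0.751)/0.25 = 1.33. At correlation 1 it is 1.00. These figures illustrate the mechanism; three questions against one is not an Aim 3 contrast.

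**3. Null simulation with continuous window exposure.** From the plan: 50 people, 14 days, 4 windows, 1 morning and 2 random prompts a day, 2 symptom questions per alert. Assumed: typical symptom probability 0.2 per question, a person intercept with SD 0.8 on the logit scale, 75% response, and alert surveys answered in about a third of windows (mean alerts per window 0.35 × exp(0.8 × exposure), at most 4). One unit of exposure is one within-person standard deviation. There were 60 runs per setting. A logistic GEE on within-person exposure stood in for the multilevel model. True odds ratio 1.00. Cells show the odds ratio, with the share of runs significant at 5% in brackets.

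| Within-window correlation | Any yes, unanswered windows dropped | Any yes, unanswered windows coded no symptom | One record per prompt | Scheduled prompts only |
|---|---|---|---|---|
| 0 | 1.304 (100%) | 1.540 (100%) | 1.001 (6.7%) | 1.008 (1.7%) |
| 0.5 | 1.130 (67%) | 1.355 (100%) | 0.996 (5.0%) | 0.999 (1.7%) |
| 0.8 | 1.064 (20%) | 1.269 (100%) | 1.016 (1.7%) | 1.005 (5.0%) |
| 1 | 1.002 (5%) | 1.197 (95%) | 1.009 (6.7%) | 0.998 (1.7%) |

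With 60 runs, the standard error of a 5% rejection rate is √(0.05 × 0.95/60) = 0.028, so the last two columns are compatible with 5%. The scheduled-only model included an indicator for more than one answered scheduled prompt. At correlation 0.5, changing the symptom probability to 0.1 or 0.4 gave 1.140 (63%) or 1.149 (97%) in the first results column.

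**4. Other ways of forming the window outcome.** Keeping the window average of all answers as a fraction gave 1.006, 1.000, 1.010 and 1.002 down the four rows. Calling a window positive when at least half its answers are yes gave 0.951 (15%) at correlation 0 and 1.002 to 1.013 in the other rows. The upward bias therefore belongs to the any-yes rule, not to windows as such.

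**The case against.** - **The averaging rule.** It applies to the extra alert surveys, and a window average kept as a fraction removes the bias. But it covers alert prompts only, does not merge them with scheduled prompts, and gives a fraction where the logistic model needs yes/no. Scoring any average above zero as yes restores the any-yes rule.
- **The prompt may be the unit.** EMA survey items lists trouble breathing, wheezing, coughing and other symptoms, so the outcome can mean any of these at one prompt. The half-hour parenthesis may tie all three outcomes to a prompt, though it may qualify FEV1 alone. On the prompt-level reading the bias does not arise. Against that, Aim 3 names windows as level 1, and Aim 2b counts time periods in which symptoms are reported. The ambiguity stands.
- **How many surveys an alert brings.** A reader might infer that every out-of-range reading adds two surveys. The monitor reads every 10 seconds, so an hour out of range would bring 360 × 2 = 720 surveys, which cannot be meant. The visible text gives no alert frequency, and the cited Appendix and figure are not available. A follow-up can also fall in the next window. The direction is clear; the number of extra questions is not.
- **Which exposures are affected.** Only mean window level varies from window to window. Threshold exceedances are counted per week and self-reported exposure is measured at baseline, so both are touched less directly. Comparing alert with no-alert windows would give more striking figures, but Aim 3 does not use that contrast.
- **Exploratory purpose.** Aim 3 explores associations in a feasibility study. This limits the consequence but does not remove the bias.

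**Conclusion.** The concern holds in conditional form. If a window's symptom outcome is any yes over its answered prompts, the Aim 3 association with window-level VOC or PM2.5 can be biased upward with no true effect, and the stated covariates do not correct it. Under the assumed rates the spurious odds ratio runs from about 1.3 per unit of exposure with independent answers to 1.0 with identical ones, and rejection from 100% to 5%. Coding unprompted windows as symptom-free is worse: 1.20 to 1.54, with 95% to 100% rejection, even when answers within a window are identical.

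A reader might go further and conclude that Aim 3 will report a positive association whatever the truth. The documents do not support that. They never state the any-yes rule, they leave room for a prompt-level reading under which the bias vanishes, and they give none of the rates that would fix its size. Because Aim 3 is exploratory, the change is recommended rather than essential.

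**What to change.** State in Data Analysis, Aim 3, that:

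1. the symptom model has one record per answered prompt, with the outcome yes if any listed symptom is reported at that prompt;
2. there are random intercepts for person and for window or day;
3. prompt type (scheduled, alert, follow-up) enters as a covariate, or a sensitivity analysis is restricted to scheduled prompts;
4. any yes over all prompts in a window is not used, and windows without a prompt are not coded as symptom-free.

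Also reconcile the two statements in EMA survey items on random surveys. One has symptoms asked in every survey; the other can be read as asking them only after disinfectant or cleaner use is reported. A scheduled-prompt outcome is free of this bias only if random surveys always ask, because otherwise the scheduled answers are themselves selected by exposure.

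The cost is analysis wording, with no new data or procedures. The prompt-level model keeps every answer; the scheduled-only version uses fewer. With prompt type as a covariate, part of the exposure contrast may be absorbed, since alert prompts occur only out of range. The two versions should therefore be read together.
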